5.5 Prior and Concomitant Therapy

Any medication or vaccine (including over-the-counter or prescription medicines, vitamins, and/or herbal supplements) that the subject is receiving at the time of Screening or receives during the study must be recorded.

Any questions regarding concomitant or prior therapy should be raised to the Sponsor Medical contact.

5.6 Prior and Post Treatment PERT Therapy

The total daily dose of Creon® taken prior to the RIV will be recorded in the electronic case report form (eCRF).

The total daily dose of Creon® taken during the Post-Treatment 30-day Period will be recorded in the eCRF.

5.7 Withdrawal of Subjects and Discontinuation of Study

A subject may voluntarily withdraw or be withdrawn from the study at any time for reasons including, but not limited to, the following:

- The subject requests to be withdrawn from the study.
- Any intake of pancreatic enzyme preparations in addition or substitution to the study drug during the study.
- When continuation of the study drug would place the subject at risk, as determined by the Investigator.
- Subjects who become pregnant during the study.
- Subject is significantly noncompliant with study procedures, which would put the subject at risk for continued participation in the study.
- Subject does not meet all continuation criteria at Day 1.

For subjects to be considered lost to follow-up, reasonable attempts must be made to obtain information on the subject's final status. At a minimum, 2 telephone calls must be made and 1 certified letter must be sent and documented in the subject's source documentation.

AbbVie may terminate this study prematurely, either in its entirety or at any site. The investigator may also stop the study at his/her site if he/she has safety concerns. If AbbVie terminates the study for safety reasons, AbbVie will promptly notify the investigator.

COVID-19 Pandemic-Related Acceptable Protocol Modification

During the COVID 19 pandemic, it may be necessary to employ mitigation strategies to enable the investigator to ensure subject safety and continuity of care. Refer to Section 2 and Section 3.1 of the Operations Manual in Appendix E.

5.8 Follow-Up After Subject Discontinuation of Study Drug or from Study

To minimize missing data for study assessments, subjects who prematurely discontinue study drug treatment should continue to be followed for all regularly scheduled visits, unless subjects have decided to discontinue the study participation entirely (withdrawal of informed consent). Subjects should be advised on the continued scientific importance of their data even if they discontinue treatment with study drug early.

If a subject prematurely discontinues study participation (withdrawal of informed consent), the procedures outlined for the Premature Discontinuation Visit (PD Visit) should be completed as soon as possible, preferably within 2 weeks. In addition, if subject is willing, a 30-day follow-up phone call after the last dose of study drug may be completed to ensure all treatment-emergent AEs/serious adverse events (SAEs) have been resolved.

5.9 Study Drug

Study drug will only be shipped to clinical sites that have provided the sponsor (or an authorized representative) with all required study documents, including Independent ethics committee/institutional review board (IEC/IRB) approval, and have signed a clinical study agreement.

Study drug capsules (**CREON-ABT** or **CREON-SPL**) will be taken orally with each meal and snack (as per patient's usual practice) with enough fluids to swallow the capsules completely. Capsules must be swallowed whole (capsules must not be crushed, chewed, or opened). Subjects will maintain throughout the study the same stable individual dose per LU of Creon they were on before initiating Screening.

If the Screening Visit and the RIV do not occur on the same day, subjects will continue their existing stable dose of commercial Creon until the RIV.

At the RIV, eligible subjects will be dispensed blinded Creon 24,000 LU manufactured with Abbott API (CREON-ABT) for the Run-in Period. At the RIV, and for the duration of the study, eligible subjects will stop using the commercial Creon 24,000 LU capsules they were taking before the RIV and begin taking the same corresponding number of capsules at meals and snacks (maintaining the same daily dosing as prescribed by their doctor), using the 24,000 LU capsules dispensed as study drug. If the subject is using more than one strength of commercial Creon capsules, the subject will keep taking the commercial Creon capsules of any other strength besides the 24,000 LU strength at the same previous dose and will switch the 24,000 LU capsules from the commercial Creon they were using before Screening to the 24,000 LU capsules dispensed as study drug.

At Day 1, subjects will return all the bottles dispensed at the RIV. Subjects who meet all continuation criteria at Day 1 will be dispensed blinded Creon 24,000 LU manufactured with SPL API (**CREON-SPL**) for the Treatment Period at the same dose used during the Run-in Period.

The subjects will be blinded to the type of study drug they will be receiving; therefore, site personnel **MUST NOT** inform the subject whether they are receiving **CREON-ABT** or **CREON-SPL** at each dispensation visit, in order to maintain the single-blind of the study.

If a subject forgets to take their study drug dose at their regularly scheduled dosing time, they should take the next dose at the next snack or meal. Information on the study drugs is provided in Table 1. AbbVie-provided study drug must not be substituted. Direct-from-patient shipping at Day 85/PD Visit is also described in the Operations Manual (Appendix E).

The subject will be instructed to return all drug containers (even if empty) to the study site personnel at the completion of the Run-in and Treatment Periods. The study site personnel will document study drug usage.

Pancrelipase (**CREON-ABT** or **CREON-SPL**) will be packaged in bottles with quantities sufficient to accommodate the study design. Each kit will be labeled per local requirements and this label must remain affixed to the kit. Upon receipt, study drug should be stored as specified on the label and kept in a secure location. Each kit will contain a unique kit number. This kit number is assigned to a subject via interactive response technology (IRT) and encodes the appropriate study drug to be dispensed at the subject's corresponding study visit. Site staff will complete all blank spaces on the label before dispensing to subjects. Study drug will only be used for the conduct of this study.

Table 1. Study Drug Information

	Investigational Product				
Investigational product name	CREON-SPL	CREON-ABT			
Product Blinded /Labeled name	Pancrelipase 24,000 USP Units (Lipase) (Creon-ABT or Creon-SPL) Delayed- Release Capsule	Pancrelipase 24,000 USP Units (Lipase) (Creon-ABT or Creon-SPL) Delayed- Release Capsule			
Type of Blinding	Single-blind (subject) ^a	Single-blind (subject) ^a			
Active ingredient	Pancrelipase, a mixture of lipase, protease and amylase of porcine origin manufactured by SPL	Pancrelipase, a mixture of lipase, protease and amylase of porcine origin manufactured by ABT			
Mode/Route of Administration	Oral	Oral			
Formulation	Pancrelipase pellets manufactured using the commercial process, with pancrelipase API sourced from SPL, filled into commercial transparent capsules with orange caps with the imprint "CREON 1224"	Pancrelipase pellets manufactured using the commercial process, with pancrelipase API sourced from ABT, filled into commercial transparent capsules with orange caps with the imprint "CREON 1224"			
Dosage Form Delayed-release Capsules		Delayed-release Capsules			
Strength	24,000 USP units (lipase) capsules	24,000 USP units (lipase) capsules			
Frequency of administration	Daily with each meal or snack	Daily with each meal or snack			
Eveinients	Capsule Shell: Gelatin, red iron oxide, sodium lauryl sulfate, titanium dioxide, and yellow iron oxide	Capsule Shell: Gelatin, red iron oxide, sodium lauryl sulfate, titanium dioxide, and yellow iron oxide			
Excipients	Drug Product: cetyl alcohol, dimethicone, hypromellose phthalate, polyethylene glycol, and triethyl citrate	Drug Product: cetyl alcohol, dimethicone, hypromellose phthalate, polyethylene glycol, and triethyl citrate			
Storage Conditions	Store between 15°C to 25°C (59°F to 77°F). See clinical label for additional details.	Store between 15°C to 25°C (59°F to 77°F). See clinical label for additional details.			

USP = United States Pharmacopoeia

Additional information on the investigational products is provided in Operations Manual Section 6.

a. Subject will not be informed whether they are receiving **CREON-ABT** or **CREON-SPL.** Study drug capsules and bottles will look identical, identifiable only by the IRT kit number.

Digital Health Tools Accountability

The investigator or his/her representative will verify that the digital health tools (e.g., PRO devices) are received intact and in the correct amounts. A proof of receipt or similar document will be kept in the site files as a record of what was received.

In addition, sites will maintain records of traceability, accountability, and return including but not limited to date received/dispensed/returned, subject number, and the identification of the person dispensing/returning the digital health tools.

5.10 Drug Assignment

This is a single-arm study, and all eligible subjects will receive both study drugs (**CREON-ABT** during the Run-in Period; **CREON-SPL** during the study Treatment Period). However, to blind subjects to the sequence of study drugs, the IRT system will be used to allocate drug.

All subjects will be assigned a unique subject identification number by the IRT at the Screening Visit. For subjects who rescreen, the subject number assigned by the IRT at the initial Screening Visit should be used.

AbbVie personnel, the investigator, study site personnel, and anyone with access to the full protocol, will be unblinded to the sequence of study drug assignment. Only subjects will remain blinded to their treatments throughout the study. To maintain the subject blind, the **CREON-SPL** and **CREON-ABT** capsules provided for the study will be identical in appearance. The investigator, study site personnel **must not** inform the subject of the order they will receive the 2 study drugs. The subject should remain blinded even if the subject experiences an AE.

5.11 Protocol Deviations

AbbVie does not allow intentional/prospective deviations from the protocol except when necessary to eliminate an immediate hazard to study subjects. The investigator is responsible for complying with all protocol requirements, written instructions, and applicable laws regarding protocol deviations. If a protocol deviation occurs (or is identified, including those that may be due to the COVID-19 pandemic), the investigator is responsible for notifying independent ethics committee (IEC)/independent review board (IRB), regulatory authorities (as applicable), and AbbVie.

5.12 Data Monitoring Committee

The external, independent data monitoring committee (DMC) will review unblinded safety data during the study. The DMC Charter for Study M21-432 will include, but is not limited to, the following: the frequency and scope of data reviews, the suggested relevant data to be included in the review, the DMC responsibilities, and the DMC members and their credentials.

Since this is a single-arm, single-blinded study and the sponsor is unblinded, the sponsor will be responsible for performing the DMC analyses described in the DMC Charter as well as any additional analyses requested by the DMC.

6 SAFETY CONSIDERATIONS

6.1 Complaints and Adverse Events

Complaints

A complaint is any written, electronic, or oral communication that alleges deficiencies related to the physical characteristics, identity, quality, purity, potency, durability, reliability, safety, effectiveness, or performance of a product/device. Complaints associated with any component of this investigational product must be reported to AbbVie.

Product Complaint

A product complaint is any complaint related to the biologic or drug component of the product or to the medical device component(s).

For a product this may include, but is not limited to, damaged/broken product or packaging, product appearance whose color/markings do not match the labeling, labeling discrepancies/inadequacies in the labeling/instructions (e.g., printing illegible), missing components/product, device damage or not working properly, or packaging issues.

Product complaints concerning the investigational product and/or device must be reported to AbbVie within 24 hours of the study site's knowledge of the event. Product complaints occurring during the study will be followed up to a satisfactory conclusion.

Medical Complaints/Adverse Events and Serious Adverse Events

An AE is defined as any untoward medical occurrence in a subject or clinical investigation subject administered a pharmaceutical product and which does not necessarily have a causal relationship with this treatment. An AE can therefore be any unfavorable and unintended sign (including an abnormal laboratory finding), symptom, or disease temporally associated with the use of a medicinal (investigational) product, whether or not the event is considered causally related to the use of the product.

Such an event can result from use of the drug as stipulated in the protocol or labeling, as well as from "special situations" such as accidental or intentional overdose, medication error, occupational or accidental exposure, off-label use, drug abuse, drug misuse, or drug withdrawal, all which must be reported whether associated with an AE or not. Any worsening of a pre-existing condition or illness is considered an AE. Worsening in severity of a reported AE should be reported as a new AE. Laboratory abnormalities and changes in vital signs are considered to be AEs only if they result in discontinuation from the study, necessitate therapeutic medical intervention, and/or if the investigator considers them to be AEs.

The investigators will monitor each subject for clinical and laboratory evidence of AEs on a routine basis throughout the study. All AEs will be followed to a satisfactory conclusion.

An elective surgery/procedure scheduled to occur during a study will not be considered an AE if the surgery/procedure is being performed for a pre-existing condition and/or the surgery/procedure has

been pre-planned prior to study entry. However, if the pre-existing condition deteriorates unexpectedly during the study (e.g., surgery performed earlier than planned), then the deterioration of the condition for which the elective surgery/procedure is being done will be considered an AE.

If any of the following events are reported, then the following supplemental reports must be completed.

Event	Supplemental Report
TEAEs compatible with clinical symptoms of EPI	EPI Symptom CRF
Covid-19 Diagnosis	COVID -19 Supplemental Signs/Symptoms CRF
	COVID-19 Status Form CRF

If an AE, whether associated with study drug or not, meets any of the following criteria, it is to be reported to AbbVie clinical pharmacovigilance or contract research organization (as appropriate) as an SAE within 24 hours of the site being made aware of the SAE (refer to Section 4.2 of the Operations Manual for reporting details and contact information):

Death of Subject	An event that results in the death of a subject.
Life-Threatening	An event that, in the opinion of the investigator, would have resulted in immediate fatality if medical intervention had not been taken. This does not include an event that would have been fatal if it had occurred in a more severe form.
Hospitalization or Prolongation of Hospitalization	An event that results in an admission to the hospital for any length of time or prolongs the subject's hospital stay. This does not include an emergency room visit or admission to an outpatient facility.
Congenital Anomaly	An anomaly detected at or after birth, or any anomaly that results in fetal loss.
Persistent or Significant Disability/Incapacity	An event that results in a condition that substantially interferes with the activities of daily living of a study subject. Disability is not intended to include experiences of relatively minor medical significance such as headache, nausea, vomiting, diarrhea, influenza, and accidental trauma (e.g., sprained ankle).
Important Medical Event Requiring Medical or Surgical Intervention to Prevent Serious Outcome	An important medical event that may not be immediately life-threatening or result in death or hospitalization, but based on medical judgment may jeopardize the subject and may require medical or surgical intervention to prevent any of the outcomes listed above (i.e., death of subject, life threatening, hospitalization, prolongation of hospitalization, congenital anomaly, or persistent or significant disability/incapacity). Additionally, any elective or spontaneous abortion or stillbirth is considered an important medical event.

All AEs reported from the time of first study drug administration until 30 days after discontinuation of study drug administration will be collected, whether solicited or spontaneously reported by the subject. In addition, study procedure-related serious and nonserious AEs will be collected from the time the subject signs the study-specific informed consent.

Adverse events will be monitored throughout the study to identify any of special interest for this study.

Adverse Events of Special Interest

The following TEAEs compatible with clinical symptoms of EPI will be considered AESI for this study:

- Diarrhea
- Abdominal pain
- Abdominal bloating
- Flatulence
- Steatorrhea

Patients with signs and symptoms suggestive of worsening EPI should be evaluated and treated as clinically indicated by the investigator.

Adverse Event Severity and Relationship to Study Drug

The investigators will rate the severity of each AE as mild, moderate, or severe.

The investigator will use the following definitions to rate the severity of each AE:

Mild The adverse event is transient and easily tolerated by the subject.

Moderate The adverse event causes the subject discomfort and interrupts the subject's

usual activities.

Severe The adverse event causes considerable interference with the subject's usual

activities and may be incapacitating or life threatening.

The investigator will use the following definitions to assess the relationship of the AE to the use of study drug:

ReasonablePossibility
After consideration of factors including timing of the event, biologic plausibility, clinical judgment, and potential alternative causes, there is sufficient evidence (information) to suggest a causal relationship to Creon

24,000 LU dispensed as CREON-ABT or CREON-SPL.

No Reasonable Possibility

After consideration of factors including timing of the event, biologic plausibility, clinical judgment, and potential alternative causes, there is insufficient evidence (information) to suggest a causal relationship to Creon

24,000 LU dispensed as CREON-ABT or CREON-SPL.

Pregnancy

While not an AE, pregnancy in a study subject must be reported to AbbVie within 24 hours after the site becomes aware of the pregnancy. Subjects who become pregnant during the study must be discontinued (Section 5.7). If a pregnancy occurs in a study subject, information regarding the pregnancy and the outcome will be collected.

The pregnancy outcome of an elective or spontaneous abortion, stillbirth or congenital anomaly is considered a SAE and must be reported to AbbVie within 24 hours after the site becomes aware of the event.

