3.3 Safety Endpoints

Safety evaluations include monitoring of treatment-emergent adverse events (TEAEs).

A TEAE compatible with the clinical symptoms of EPI will be considered an adverse event of special interest (AESI) for this study and will be summarized separately.

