10.2.6 Adverse Events of Special Interest

Adverse events of special interest will be summarized by SOC and PT. The following TEAEs compatible with clinical symptoms of EPI will be considered as Adverse Events of Special Interest (AESI) for this study:

- Diarrhea
- Abdominal pain
- Abdominal bloating
- Flatulence
- Steatorrhea

Detailed information about the search criteria is in Appendix B.

Tabular listings of adverse events of special interest will be provided.

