Appendix B. Definition of Adverse Events of Special Interest

Adverse Events of Special Interest (AESI) will be identified using the following search criteria:

[figure not shown]
Adverse Event of Special Interest	Preferred Terms
Diarrhea	Diarrhoea
	Diarrhoea haemorrhagic
	 Diarrhoea infectious
	Defaecation urgency
	 Frequent bowel movements
	 Gastrointestinal hypermotility
	 Faecal volume increased
	 Overflow diarrhoea
Abdominal pain	Abdominal discomfort
	Abdominal Pain
	 Abdominal pain lower
	 Abdominal pain upper
	Gastrointestinal pain
Abdominal bloating	Abdominal distension
	 Gastrointestinal sounds abnormal
Flatulence	Flatulence
Steatorrhea	Faeces pale
	Faecal fat increased
	Faeces discoloured

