Appendix C. Pancreatic Exocrine Insufficiency Questionnaire (PEI-Q)

This questionnaire asks about problems you may experience if you do not produce enough enzymes to digest your food.

AB	DOMINAL SYMPTOMS	NO NOT AT ALL	YES, A LITTLE BIT	YES, SOME	YES, QUITE A BIT	YES, A LOT	SCORE	
1.	In the past 7 days, did you have stomach pain?	0	1	2	3	4		
2.	In the past 7 days, did you feel bloated (your stomach feeling tight and full)?	0	1	2	3	4		
3.	In the past 7 days, did your stomach make noises?	0	1	2	3	4		
4.	In the past 7 days, did you pass gas?	0	1	2	3	4		
5.	In the past 7 days, when you passed gas did it smell bad?	0	1	2	3	4		
6.	In the past 7 days, did you feel sick (but didn't actually vomit/throw up)?	0	1	2	3	4		
7.	In the past 7 days, did you have a lack of appetite?	0	1	2	3	4		
		Sum of abdominal symptom scores:						
	Mean abdominal symptom domain score (A):							
во	WEL MOVEMENT SYMPTOMS	NO NOT AT ALL	YES, A LITTLE BIT	YES, SOME	YES, QUITE A BIT	YES, A LOT	SCORE	
BC 8.	WEL MOVEMENT SYMPTOMS In the past 7 days, did you have diarrhea (watery poo)?						SCORE	
	In the past 7 days, did you have diarrhea	AT ALL	LITTLE BIT	SOME	A BIT	A LOT	SCORE	
8. 9.	In the past 7 days, did you have diarrhea (watery poo)? In the past 7 days, did you feel the need to rush to the toilet to have a bowel	AT ALL 0	LITTLÉ BIT	SOME 2	A BIT	A LOT	SCORE	
8.9.10.	In the past 7 days, did you have diarrhea (watery poo)? In the past 7 days, did you feel the need to rush to the toilet to have a bowel movement (have a poo)? In the past 7 days, did your poo look	0 0 0	1 1	SOME 2	3 3	4 4	SCORE	
8.9.10.11.	In the past 7 days, did you have diarrhea (watery poo)? In the past 7 days, did you feel the need to rush to the toilet to have a bowel movement (have a poo)? In the past 7 days, did your poo look lighter or orange in color? In the past 7 days, when you had a poo	0 0 0 0 0 0 0 0 0 0 0 0 0 0 0 0 0 0 0		2 2 2	3 3 3 3	4 4 4	SCORE	
8.9.10.11.	In the past 7 days, did you have diarrhea (watery poo)? In the past 7 days, did you feel the need to rush to the toilet to have a bowel movement (have a poo)? In the past 7 days, did your poo look lighter or orange in color? In the past 7 days, when you had a poo did it smell bad? In the past 7 days, did you see or have fat	0 0 0 0 0 0 0 0 0 0 0 0 0 0 0 0 0 0 0		2 2 2 2 2	3 3 3 3 3 3 3 3 3 3 3 3 3 3 3 3 3 3 3	4 4 4 4	SCORE	

18. In the past 7 days, did your **enzyme problems** affect your **social activities**?

	Version 2.0 – 20 July 2023						_

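### An adverse event recorded as worsening EPI or malabsorption falls outside the AESI search, which covers only five component symptoms

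*Protocol*

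**What the plan says.** Protocol 3.3 describes the AESI openly: "A TEAE compatible with the clinical symptoms of EPI will be considered an adverse event of special interest (AESI) for this study". SAP 3.2 says the same. Neither gives a list.

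Protocol 6.1 gives the list. After "The following TEAEs compatible with clinical symptoms of EPI will be considered AESI for this study" it names diarrhea, abdominal pain, abdominal bloating, flatulence and steatorrhea. The next sentence turns to deterioration of the disease itself, but only as a matter of care: "Patients with signs and symptoms suggestive of worsening EPI should be evaluated and treated as clinically indicated by the investigator". Earlier in the same section stands the general rule "Any worsening of a pre-existing condition or illness is considered an AE".

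SAP 10.2.6 repeats the five symptoms and adds "Detailed information about the search criteria is in Appendix B". Appendix B opens with "Adverse Events of Special Interest (AESI) will be identified using the following search criteria" and assigns preferred terms to each of the five.

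Protocol 6.1 also requires a supplemental EPI Symptom CRF for EPI-compatible treatment-emergent events. It gives no term list beside that requirement.

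**The concern.** Every subject enters with diagnosed and currently controlled EPI (Protocol 5.1, criterion 6), so under the rule on pre-existing conditions a deterioration of EPI is a reportable adverse event. A site may record it as its symptoms or as the diagnosis. Recorded as symptoms, it reaches the AESI summaries. Recorded as the diagnosis, it matches none of the five names and none of the Appendix B terms. The same clinical event is then counted or not depending on how it was written down. Infectious diarrhea, meanwhile, is on the search list.

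The AESI group is the only safety category in the plan that gathers EPI-type events. The PEI-Q does not fully replace it: it has a 7-day recall and is completed on CREON-SPL at Days 8, 15, 29 and 85. Those windows cover 4 × 7 = 28 of the 84 days from Day 1 to Day 85. The other 56 days rest on adverse event reporting.

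**Working it through.** No figure in the plan needs to be reproduced here. The check sets the definitions side by side and follows one event through them.

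**1. The search list.** Terms in SAP Appendix B, as they appear in the text available:

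- Diarrhea: 8
- Abdominal pain: 5
- Abdominal bloating: 2
- Flatulence: 1
- Steatorrhea: 3

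Total: 8 + 5 + 2 + 1 + 3 = 19. Terms that refer to the pancreas, to insufficiency or to malabsorption: 0.

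**2. One event followed through.** Suppose a subject on CREON-SPL deteriorates and the site enters worsening of EPI as the event.

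- Protocol 6.1, pre-existing conditions: it is an adverse event.
- SAP 10.2.1: with onset on or after the first CREON-SPL dose and within 30 days of the last, it is treatment-emergent.
- Protocol 3.3 and SAP 3.2: it fits the general wording, so it is an AESI.
- Protocol 6.1 list and SAP 10.2.6: it is none of the five symptoms, so it is not an AESI.
- SAP Appendix B: no term matches, so the search does not find it.
- EPI Symptom CRF: the site could reasonably complete the form, since its trigger uses the general wording. The search would still not count the event.

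**3. Outputs affected.** SAP 10.2.2 has two AESI rows in the overview (all, and those with a reasonable possibility of relation to drug). The overview is produced three times: main, restricted to 28 days, and per 100 patient-years. That is up to 2 × 3 = 6 rows for each safety set, plus the AESI table by SOC and PT and the AESI listing of SAP 10.2.6.

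**4. Outputs not affected.** The event appears in the tables by SOC and PT, by maximum severity and by relationship (SAP 10.2.3), in the rates by preferred term (SAP 10.2.4) and, if it qualifies, in the tables and listings of serious events and of events leading to discontinuation (SAP 10.2.5).

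**5. Size.** For the subject percentages, the shortfall is x/N. Here N is the size of the safety set, and x is the number of subjects whose only EPI-compatible event was recorded as the diagnosis. A subject who also reports a listed symptom is already counted and does not add to x. For the rates, SAP 10.2.4 counts every occurrence. If that definition carries over to the overview, each diagnosis-recorded event is missing from the numerator even when the subject has another AESI. The documents give no expected event rates, so neither quantity can be computed.

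**The case against.** The strongest reply is that the general wording was never meant to stand alone. Protocol 7.5 uses the same general phrase and points to Section 6.1, so Section 3.3 can be read as a summary and the 6.1 list as its definition. That stands, and it means the documents do not flatly contradict each other. It does not close the gap: the list, read as the definition, still leaves out the condition whose symptoms it is meant to capture.

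The second reply is that nothing disappears. With about 30 subjects enrolled, a reader of the preferred-term tables would see an event of worsening EPI. This also stands, and it limits the point to the AESI outputs.

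Third, the content of the EPI Symptom CRF is not shown. It may break a diagnosis down into component symptoms, but whether those would then feed the search cannot be judged.

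A reader might go further and argue that nausea and loss of appetite must be AESIs because the PEI-Q scores them: "In the past 7 days, did you feel sick (but didn't actually vomit/throw up" and "In the past 7 days, did you have a lack of appetite". The two items carry 2 × (1/7 × 1/2) = 1/7, or about 14%, of the Total Symptom Score. But no passage says that AESIs must mirror the questionnaire. Both symptoms are already scored in the ASDS and TSS, and an item weight says nothing about adverse event counts. Leaving two less specific symptoms off the list is a legitimate choice.

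**Conclusion.** The point holds as a gap in coverage. An event recorded as worsening or loss of control of EPI, or as malabsorption, meets the general AESI description in Protocol 3.3 and SAP 3.2 but is not counted under Protocol 6.1, SAP 10.2.6 and Appendix B. The AESI summaries can understate EPI-compatible events; the other safety tables are unaffected. In a descriptive study with no hypothesis test this is a cheap improvement, not a threat to the main results.

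Two stronger readings lack support. One is that the plan would miss a deterioration of EPI altogether, or miss the most serious events: all treatment-emergent events are tabulated, and nothing in the documents ranks these as most serious. The other is a shift of a stated number of percentage points: any such figure would rest on an assumed event count.

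The conclusion assumes that Appendix B is complete as extracted. Its steatorrhea row shows no term for steatorrhea itself, so the table should be checked against the original. It also assumes that sites are not told elsewhere, for example in the Operations Manual, to record only component symptoms. The five-symptom list in Protocol 6.1 does not depend on the extraction of Appendix B.

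**What to change.** - **Search list.** Add to Protocol 6.1, SAP 10.2.6 and Appendix B a prespecified set of preferred terms for exocrine pancreatic insufficiency (including its worsening) and for malabsorption, named from the MedDRA version in use. Keep it a fixed term search. Case-by-case classification from the reported wording would put judgement in the hands of a sponsor who knows the drug sequence (Protocol 5.10).
- **Both products.** Apply the same terms to CREON-ABT and CREON-SPL, and in all three versions of the overview.
- **Presentation.** Show the new terms as their own row, so that the five-symptom total can still be read.
- **CRF trigger.** Tie the EPI Symptom CRF requirement in Protocol 6.1 to the same list, so that what sites flag and what the SAP counts agree.

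The cost is a few search terms run on adverse event data that are already collected and coded. The protocol wording would need the ethics review that Protocol 8.1 requires for any amendment, and a changed CRF trigger helps only for events still to be reported. The SAP is already at version 2.0, dated 20 July 2023, so its version history should say that the row was added late.
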